1.3 Secondary Study Endpoints

N/A

2.0 Background

2.1 Scientific Background and Gaps

Although half of the 37 million adult smokers in the US attempt to quit each year, only an estimated 3% are successful.^{1,2} This is why smoking continues to be the leading cause of preventable death in the US, killing nearly half a million people each year from tobacco-related causes.³ Given that approximately 70% of smokers report a desire to quit, there is a critical need for improved neuropharmacological cessation aids to assist current smokers in quitting and to inform FDA regulations aimed at preventing highly addictive tobacco products from reaching the market.²

A key neurobehavioral component that contributes to the development of cigarette addiction is the conditioned associations that form between smoking stimuli and the rewarding dopaminergic effects of nicotine.⁴ Associative learning is driven primarily by cellular and circuit-level changes in the mesocorticolimbic (e.g., hippocampus, amygdala, nucleus accumbens) and prefrontal brain structures.^{4,5} Associations between stimuli and nicotine are strengthened with each puff of a cigarette.⁴ Ultimately, sensory smoking cues trigger positive expectancies of smoking and contribute to their high addictive potential.⁶ In other words, the salience of these smoking cues becomes heightened. This is why non-nicotine factors significantly contribute to cigarette dependence.^{6,7} Animal research has shown that nicotine-associated cues can impede cessation even with pharmacological treatment.⁸ Using fMRI, blood-oxygen-level-dependent (BOLD) reactivity to nicotine-associated smoking stimuli has been linked to less control over cravings⁹, reductions in withdrawal symptoms¹⁰, and increased ad lib smoking during laboratory tasks.¹¹ We currently have a limited understanding of how the salience of smoking cues, measured via cue-reactivity, is affected by tobacco products varying in nicotine content the use of cessation aids.

While the salience of smoking cues increase for dependent smokers, the salience of non-smoking incentives, such as money, food, and socioemotional stimuli, is diminished.¹² This is evident by smokers' attenuated neural reactivity to the anticipation and receipt of monetary and food rewards during laboratory tasks compared to non-smokers.¹³⁻¹⁵ In addition, smokers show executive dysfunction in sustained attention, working memory, and inhibitory control processes during acute abstinence that are integral to maintaining goal-directed behavior during withdrawal.¹⁶⁻²⁰ Executive control brain circuitry primarily includes the lateral and medial prefrontal cortex, anterior cingulate (ACC), superior and inferior parietal cortices, and in some cases subcortical structures.²¹ There is considerable overlap and communication between the circuitry involved in executive control and incentive salience valuation.²²⁻²⁴ Impairments in inhibitory control and working memory have been associated with relapse during quit attempts^{25,26} and nicotine replacement therapy alleviates executive dysfunctions during withdrawal.²⁷ We are just beginning to understand how the circuitry underlying incentive salience and executive control work together to influence smoking dependence and treatment outcomes.^{13,28,29}

We currently know little about how neural activity and connectivity of the incentive salience and executive control circuitry change during cessation treatment. Given the advancements in pharmacotherapy and non-invasive brain stimulation techniques,^{30,31} gaining a nuanced understanding of how brain circuitry adapts during rehabilitation could identify neural targets for treatment. Verenicline and bupropion treatment are associated with reductions in neural activity throughout prefrontal brain circuitry during executive control and cue-reactivity tasks, respectively.^{32,33} However, given the reductions in dependence for the control groups, these neural changes were likely due to the effects of the medication, not changes in dependence.^{32,33} Very low nicotine content (VLNC) cigarettes have been used as an extinction-based cessation treatment to reduce the rewarding effects of cigarettes by significantly reducing nicotine delivery during smoking.^{6,34} Smokers rate de-nicotinized cigarettes as satisfying and trials of VLNC cigarettes result in decreases in the number of cigarettes smoked per day and self-reported dependence.³⁵ VLNC cigarettes provide a unique opportunity to assess changes in neural circuitry while smokers extinguish the association between nicotine and smoking stimuli and become less dependent on smoking without the confounding effects of nicotine replacement therapy or pharmacotherapy.

The current study will examine functional neuroadaptations in incentive salience and executive control circuitry while smokers switch to VLNC cigarettes over 6-weeks. Identifying brain circuitry that is

modified at various stages of recovery can lead to the development of targeted neuropharmacological cessation aids and brain stimulation techniques. The findings of the proposed study will characterize changes associated with the extinction of conditioned cues and reductions in dependence without the confounding effects of pharmacological aids. By measuring neural processes and connectivity among circuitry mid-intervention, the results of the proposed study will pinpoint aspects of neural circuitry that are sensitive to (or reflective of) early intervention effects.

2.2 Previous Data

The Penn State Center for NMR Research (CNMRR) has pioneered the study of human olfaction, including circuitry involved in the detection and perception of odor³⁶ and links to motivation, learning, and reward.^{37,38} [name] mentee, [name], conducted preliminary work showing that the scent of fresh tobacco induced higher subjective craving and skin conductance compared to a no-odor control condition.³⁹ Using fMRI, pairing smoking odor and visual cues significantly enhanced cue-reactivity throughout frontal and temporal cortices, which was linked to control over craving.⁹ The proposed study will extend [name] preliminary work by examining how smoke flavor (i.e., odor and taste) is modified by intervention and associated with dependence and cessation outcomes.

In preliminary work conducted by the Penn State Tobacco Center of Regulatory Science (TCORS) we found that resting state functional connectivity decreased in key regions involved in executive control (frontal pole), reward valuation (anterior cingulate) and craving (insula and thalamus) after nicotine administration with an e-cig.⁴⁰ Weaker coupling between reward and executive control networks was associated with less craving after use.⁴⁰ This cross-sectional pilot study demonstrated that flavored electronic cigarettes altered brain connectivity among brain regions involved in the development of smoking dependence. The current study extends this work to determine if flavor, without nicotine, is a central feature of the development of smoking dependence.

A 0.4 mg cigarette will be used in the current study to maximize efficacy for reducing smoking dependence and rates of compliance and retention, while minimizing the chance of compensatory smoking. In a large clinical trial, reduced nicotine content (RNC) cigarettes of 0.4 mg were associated with the largest reductions in the number of cigarettes smoked per day, urinary nicotine, and subjective ratings of withdrawal and dependence compared to all other nicotine contents.³⁵ A separate study found that cigarettes at 0.3 mg increased compensatory smoking over 0.5 mg cigarettes.⁴¹ Preliminary results from the Penn State RNC trial with low socioeconomic status (SES) smokers shows that ratings of cigarette satisfaction only dropped 38% over the 7-month trial despite the 97% reductions in nicotine content, which likely contributes to their high rates of compliance and retention. In addition, preliminary fMRI research has shown that RNC cigarettes (2.4 mg) paired with a 21 mg nicotine patch was related to reductions in BOLD activation to smoking-related cues and increased activation to neutral cues in the amygdala after only 2 weeks.³⁴ Reduced activation in the thalamus over the course of intervention was predictive of improved cessation outcomes in a post-treatment quit attempt.³⁴

2.3 Study Rationale

Tobacco use is the leading cause of preventable death in the U.S.³ Smoking dependence is in part maintained by three interrelated cognitive processes; 1) enhanced incentive salience of smoking stimuli^{42,43}, 2) diminished incentive salience of non-smoking rewards,^{14,44,45} and 3) impairments in executive control²⁵. These interrelated processes lead to poorly controlled motivational drives to smoke and contribute to smoking maintenance and relapse during quit attempts.^{46,47}

The incentive salience, or motivational value, of conditioned smoking stimuli becomes enhanced for regular smokers.⁴⁸ This is evident in the subjective and physiological reactivity smokers show in response to smoking-related cues.⁴⁹ In the laboratory, visual, tactile, and auditory smoking stimuli can elicit strong cigarette craving, shorter latency to smoking, and more frequent, higher volume cigarette puffs.⁵⁰ Flavor, a combination of odor and taste, is one smoking stimuli that has interested tobacco companies for its potential to increase dependence on cigarettes.^{51,52} Despite evidence supporting the role of flavor in addiction and the rising popularity of new flavored tobacco products, we currently know little about the neurobiological impact of flavor on the development and maintenance of smoking dependence. This

is a research priority for NIH's Tobacco Regulatory Science Research Program due to its potential to inform tobacco policy.⁵³

Alternatively, the salience of non-smoking incentives, such as money, food, and socioemotional stimuli, is diminished among smokers.¹² This is evident by smokers' attenuated neural reactivity to the anticipation and receipt of monetary and food rewards during laboratory tasks compared to non-smokers.¹³⁻¹⁵ Attenuation of reward reactivity, most notable in the striatum during states of acute smoking abstinence, has been associated with relapse during cessation attempts.^{14,15,54}

In addition to changes in incentive salience, there is growing evidence that smoking dependence is characterized by weakened executive control, in which "top-down" systems fail to inhibit the "bottom-up" incentive salience processes that drive smoking motivation.^{17,55} Smokers show executive dysfunction in sustained attention, working memory, and inhibitory control processes during acute abstinence that are integral to maintaining goal-directed behavior during withdrawal.¹⁶⁻²⁰

We currently know little about how neural activity and connectivity of the incentive salience and executive control circuitry change during recovery. Given the advancements in pharmacotherapy and non-invasive brain stimulation techniques,^{30,31} gaining a nuanced understanding of how brain circuitry adapts during rehabilitation could identify neural targets for treatment. VLNC cigarettes have been used as an extinction-based cessation treatment to reduce the rewarding effects of cigarettes by significantly reducing nicotine delivery during smoking.^{6,34} Over the course of a VLNC extinction trial with nicotine replacement therapy, smokers' reactivity in the amygdala to smoking over neutral visual cues decreased.³⁴ Participants who successfully abstained in a quit attempt following the extinction trial had reduced cue reactivity in the thalamus and ventral striatum compared to participants who relapsed.³⁴

The central hypothesis underlying this award is that brain circuitry associated with incentive salience valuation and executive control can be altered by treatment interventions and, consequently, serve as potential biomarkers of dependence reduction and cessation treatment outcomes. In a double-blind, randomized controlled trial, dependent smokers will be randomized to a 6-week VLNC cigarette intervention (N=50) or a 6-week normal nicotine content cigarette control condition (NNC; N=25). Participants will undergo fMRI scans at baseline, and 6-weeks to investigate the treatment-related modulation of brain circuitry involved in incentive salience valuation and executive control. Imaging tasks will assess the incentive salience of smoking cues and non-smoking rewards and executive function to identify changes in functional activity within, and effective connectivity between, known salience and executive control brain circuitry. A novel fMRI task using specialized odor presentation equipment and fMRI sequences will assess neural cue reactivity to smoke odors.

3.0 Inclusion and Exclusion Criteria

3.1 Inclusion Criteria

1. 21-60 years old
2. Smoke ≥5 cigarettes per day
3. >1 year of daily smoking
4. No quit attempt in prior month and not planning to quit smoking within next 3 months
5. Able to understand and consent to study procedures
6. Educational attainment < college degree or annual household income < \$50,000
7. Plan to live in local area next 3 months
8. Women not pregnant or nursing and not planning to become pregnant in the next 3 months
9. Able to read and write in English
10. Access to computer with internet service that allows for Zoom

3.2 Exclusion Criteria

1. Use of non-cigarette tobacco products in the past 7 days
2. Use of illicit substances more than once a week in the past 3 months (excluding marijuana)
3. Current alcohol abuse impairing participation

4. MRI safety contraindications (e.g., metal implants, claustrophobia)
5. Unstable or significant medical conditions (e.g., COPD, coronary heart disease)
6. Major neurological conditions or brain trauma
7. Major surgeries planned in next 3 months
8. Use of smoking cessation medication in prior month (e.g., varenicline, patch)
9. Uncontrolled serious mental illness, suicidality, or inpatient psychiatric hospitalization in the past 6 months
10. Unwillingness to provide urine samples
11. Unwilling to smoke study assigned cigarettes for the remainder of the trial
12. Plans to move or take extended travel out of the area in the next 3 months
13. Any other condition or situation that would, in the investigator's opinion, make it unlikely that the participant could comply with the study protocol
14. Self-reported color blindness
15. Left-handedness
16. Smell dysfunction as determined via standardized assessment

3.3 Early Withdrawal of Subjects

3.3.1 Criteria for removal from study

- Excessive visit cancellations or no-shows.
- Inability to attend the study visit within the allowed visit window.
- Inability or unwillingness to smoke study cigarettes.
- Lost contact.
- Pregnancy (confirmed by urinary pregnancy test at each MRI visit).
- Suicide attempts
- Cardiovascular (CVD) event: including MI (heart attack), PTCA (angioplasty/stenting), bypass surgery, stroke, peripheral vascular disease, arrhythmias and new valvular disease (e.g., mitral or aortic regurgitation).
- DVT/PE (deep vein thrombosis/pulmonary embolism)
- Participants may choose to remove themselves from the study by informing the research team at any point during the study.
- Significant baseline smoking rate increase at 3-week check-in or post-scan visit. Either one, or both criteria combined:
 - The average CPD increases by more than 100% from the average CPD on the baseline cigarette log.
- Worsening substance use in which the participant is behaving inappropriately at visits or demonstrates an inability to continue with the study.
- Any hospitalization in which participation in the study could be detrimental to the recovery process. (e.g., recovery from a major surgery, etc.)
- Any situation where participant is not able to smoke research cigarettes for a period of more than 3 days
- Participant doesn't comply with the protocol, behaves in an inappropriate or threatening manner, admits to lying about eligibility criteria, or is participating in other smoking research studies that could affect the primary outcome measures.

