3.3.2 Follow-up for withdrawn subjects

Participants who report an inability to smoke research study cigarettes will be asked to complete a final MRI scan visit before being withdrawn from the study.

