- Prior to the visit, an unblinded member of the study team will randomize the participant to either the VLNC or NNC cigarette group based on a pre-determined block randomization list. The unblinded study member will identify the cigarette packs with the assigned nicotine content by NRC code and prepare them for redistribution by re-labeling each pack with the participant ID number and a label indicating these are research cigarettes. The unblinded study member will keep records of the RTI log numbers of the packs dispensed to each participant at each visit. At the end of MRI Visit 1 participants will be given an ample 6-week supply of their assigned cigarette (125% of baseline cigarettes per day) and instructed to only smoke study cigarettes until their next scheduled appointment. Participants may contact the study team to receive more study cigarettes if they run out prior to their next visit unless this is more than a 100% increase from their baseline CPD. Participants will be instructed to continue completing the daily REDCap cigarette log surveys that they receive via text message and will also be given paper cigarette logs to track use throughout the day.

Time commitment: 2 hours

7.2.3 Remote visit 1 (scheduled for +1 to +3 day(s) of in person MRI visit)

Participants will complete the following procedures over Zoom

1. REDCap Survey Questionnaire

- a. Depression (CESD)
- b. COPD (CCQ)
- c. Psychological Distress (Kessler K6)
- d. Nicotine Dependence
- e. Anxiety (ASQ)
- f. Sleep Disturbance
- g. Cigarette Liking
- h. Stages of Change
- i. Perceived Stress

2. Interview

- a. Concomitant medications
- b. Adverse event trigger questions

3. Out of scanner tasks

- a. Participants will complete a monetary temporal discounting task. During this computerized task, participants will choose between two options with specified dollar amounts and time delays to receipt of money (see MRI task image below).
- b. Participants will complete a computerized stroop interference task where they will view color words printed in the same color (i.e., blue, red, yellow, green), color words printed in an incongruent color (e.g., “blue” printed in red), and color neutral words printed in color (e.g., “hat” printed in red). Participants will be asked choose what color each word is printed in by pressing a button labeled to indicate each color.

7.2.4 Phone call 1

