7.2.5 Remote visit 2 (Week 3 ± 5 days)

Participants will complete a Zoom call three weeks into the randomization phase. During this visit participants will complete the following activities:

1. Review cigarette tracking logs with study staff.
2. Concomitant medication
3. Adverse event trigger questions
4. Discuss and problem-solve barriers to adherence
5. Computerized REDCap Survey Questionnaires (see Remote Visit 1 and MRI Visit 1)
6. Complete computerized out-of-scanner tasks.

Time commitment: 1 hours

Participants will be asked to refrain from smoking for 14 hours prior to MRI visit 2. The MRI visit 2 and Remote visit 3 will be scheduled.

7.2.6 Phone call 2

Participants will be contacted in the 4th week of the randomization phase to check-in regarding their next scheduled appointment and their success with cigarette tracking and study cigarette compliance.

Time commitment: 15 minutes

7.2.7 Remote visit 3 (scheduled for -1 to +1 day of in person MRI visit)

Participants will complete the following procedures over a Zoom call

1. Concomitant medications
2. Adverse event trigger questions
3. Perceived health risk rating
4. Computerized REDCap Survey Questionnaires (see Remote Visit 1)
5. Review cigarette tracking logs.
6. Complete computerized out-of-scanner tasks
7. Complete quit choice survey and counseling. Participants will be reminded that they will receive a text message survey in 12 weeks asking for information on quit attempts.

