7.2.8 MRI visit 2 (Week 6 ± 5 days)

Participants will return to the CNMRR Center for their final MRI scan after refraining from smoking for 14 hours prior to the visit.

For the final study visit, participants will complete the following activities:

1. Return all (empty and full) cigarettes packs
2. Penn State CNMRR MRI safety and Scent Ratings (post MRI)
3. Urine collection for cotinine analysis and pregnancy determination: Obtain urine and process pregnancy test for women of child bearing age (have had a period in the past 12 months) who have not had a hysterectomy
4. Saliva collection for potential cotinine analysis, micro RNA (miRNA) biomarker analysis, and use in future research.
5. Exhaled carbon monoxide will be measured using a hand-held monitor.
6. Computerized REDCap Survey Questionnaires (nicotine withdrawal, smoking urges, craving)
7. The MRI technologist will first review the MRI safety sheet and determine that it is safe for the participant to be scanned. If safe, participants will complete a one-hour MRI scan.

Time commitment: 2 hours

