Aim 3: Establish measurable and objective neural outcomes of successful reductions in smoking dependence. FSL's Randomise one-sample t-test will be conducted on change scores to determine if changes in BOLD activity are associated with reductions in subjective markers of dependence (FTND, HONC, MNWS, QSU), cigarettes smoked per day, and quit intention and success. Changes in connectivity estimates will be correlated with changes in subjective and behavioral outcomes.

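### Participants who become unwilling to smoke the assigned product are removed after randomisation with no stated end-of-treatment scan or dependence assessment, and the return visit for those unable has no timing and does not name Remote visit 3

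*Combined protocol and SAP*

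**What the plan says.** Section 3.3.1 has two removal criteria that concern use of the assigned product: "Inability or unwillingness to smoke study cigarettes" and "Any situation where participant is not able to smoke research cigarettes for a period of more than 3 days".

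The whole follow-up rule for withdrawn participants is one sentence in Section 3.3.2: "Participants who report an inability to smoke research study cigarettes will be asked to complete a final MRI scan visit before being withdrawn". It gives no week for that visit, does not mention the unwilling, and names no other contact.

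The end-of-treatment data come from two contacts:

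- MRI visit 2 (Section 7.2.8, week 6 ± 5 days) collects the scan, urine, saliva, exhaled carbon monoxide, returned packs and "Computerized REDCap Survey Questionnaires (nicotine withdrawal, smoking urges, craving".
- Remote visit 3 (Section 7.2.7) repeats the Remote visit 1 questionnaires, which include "Nicotine Dependence" (Section 7.2.3, item d), and adds the quit choice survey. Its heading reads "Remote visit 3 (scheduled for -1 to +1 day of in person MRI visit".

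A text survey on smoking status and quit attempts follows at week 18 (the second section numbered 7.2.7).

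Section 1.2 gives two primary endpoints: change in neural reactivity to tobacco odor and change in smoking dependence. Section 8.3 (Aim 3) relates BOLD change to "subjective markers of dependence (FTND, HONC, MNWS, QSU), cigarettes smoked per day, and quit intention and success".

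**The concern.** Rejecting the product happens after randomisation and may be a response to it. The arms differ in nicotine content (11.6 mg against 0.29 mg, Section 7.4.1), and Section 11.0 names withdrawal symptoms as a risk of reduced nicotine, so the frequency of rejection, or the kind of person who rejects, could differ by arm. If those people leave with no week-6 data, the participants compared at week 6 are no longer the randomised groups.

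Two parts of the analysis are exposed. The first is the between-arm comparison of activation (Aim 1) and connectivity (Aim 2). The second is the set of Aim 3 associations, which need a change score for both brain and behaviour in the same person. Section 8.3 states no analysis set and no method for missing data. Recruiting until 75 people complete (Section 8.2) restores the number but not the comparability of the arms.

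The boundary between unable and unwilling is also not defined. Two people who stop for much the same reason could be handled differently depending on how they phrase it.

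**Working it through.** **1. Removal follows randomisation.** Under Section 7.2.2 the participant is randomised before MRI visit 1 and receives the assigned cigarettes at the end of that visit. Nobody can meet either product-use criterion before then.

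**2. What is requested at the end of treatment, by group**

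| Group | Scan | Withdrawal, urges, craving | Nicotine Dependence, quit choice survey | Week-18 survey |
|---|---|---|---|---|
| Completers | Week 6 ± 5 days | Yes | Yes (Remote visit 3) | Yes |
| Removed, report inability | Asked, no timing | Yes, with the scan visit | Not named; may be intended | Not named |
| Removed, unwilling | None stated | None stated | None stated | None stated |

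**3. Aim 3 dependence scales.** Section 8.3 lists four: FTND, HONC, MNWS and QSU. MRI visit 2 lists withdrawal and urges, which Section 7.2.2 labels MNWS and QSU. On the strict reading of Section 3.3.2, a participant reporting inability supplies 2 of 4, and an unwilling participant supplies 0 of 4. The visit schedule does not name FTND or HONC. That they make up the Nicotine Dependence item is an assumption.

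**4. Timing.** Section 8.3 compares baseline with 6-week scans. An exit scan taken, say, at week 2 reflects a different exposure and does not fit that contrast. Section 3.3.2 does not say which is meant.

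**5. Number exposed.** The plan's own retention figure reproduces: 0.80 × 75 = 60 (Section 8.2). However, the same section recruits until there are 75 completers and expects about 90 to consent, so the relevant count is:

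- 90 − 75 = 15 losses at most. The 90 includes people later found ineligible, so losses after randomisation should be fewer.
- At the cited 92% retention: 75/0.92 = 81.5 randomised, 6.5 lost.
- At the cited 85% retention: 75/0.85 = 88.2 randomised, 13.2 lost.
- At 80%: 75/0.80 = 93.75 randomised, which exceeds 90. This case does not fit the plan and is set aside.

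With 2:1 allocation and equal loss rates (an assumption), 6.5 losses split as 4.3 VLNC and 2.2 NNC, 13.2 as 8.8 and 4.4, and 15 as 10 and 5. All of these count every reason for loss.

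**6. Why no bias figure follows.** Let p be the share of an arm lost through this criterion, and d the mean outcome of those retained minus the mean of those lost. The retained mean then differs from the mean of everyone randomised by p × d. The between-arm bias is p(VLNC) × d(VLNC) − p(NNC) × d(NNC). It is zero if both terms are equal. All that can be bounded is the overall all-cause share, at most 15/90 = 17%. The documents give no p by arm for this criterion, and no d.

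**The case against.** The strongest case on the other side has five parts.

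- **Remote visit 3 is probably implied.** It is timed to the MRI visit, not to a study week, so asking for a final MRI visit may bring it along. This stands for participants reporting inability, and the need there is only to name the visit. It does not help the unwilling, who are not asked for an MRI visit at all.
- **Much is still collected.** Those reporting inability give the scan, withdrawal, urges, craving, cotinine and carbon monoxide. Anyone removed after week 3 already has a Nicotine Dependence score from Remote visit 2. Both points stand. The week-3 score is not an end-of-treatment score, however.
- **No between-arm test of dependence is stated.** Section 8.3 uses dependence only in the Aim 3 associations. This stands, so a reader should not infer that a planned between-arm dependence comparison is biased. Selective loss can still distort an association between change scores, and the between-arm imaging comparisons remain exposed.
- **The unwilling should be few.** Exclusion 11 in Section 3.2 screens out those unwilling to smoke the product, participants may smoke as little as they like (Section 7.4.6.3), and contacts in weeks 2, 3 and 4 cover compliance. This limits the number, but the screen comes before any experience of the assigned cigarette.
- **This is a mechanistic study, and off-product scans blur the contrast.** That is a fair trade-off. But Section 3.3.2 already asks for scans from people who cannot smoke the product, so the plan itself values them. No rule can compel the unwilling to return; at present they are not asked.

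**Conclusion.** The point holds as a cheap improvement. The firm gap is the missing week-6 scan and end-of-treatment questionnaires for participants who become unwilling. The lesser gap is that the return visit for those unable has no timing and does not name Remote visit 3. At most about 15 people are lost after randomisation from all causes, on the plan's figures of about 90 consented and 75 completers, and this criterion accounts for an unknown part of them.

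Three stronger inferences are tempting and not supported:

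- **That the rule biases the trial in a known direction, for example by removing more VLNC participants.** This is plausible, but the documents give no removal rate by arm.
- **That the dependence endpoint is lost for everyone removed.** Participants reporting inability supply at least withdrawal and urges, and Remote visit 3 may be intended for them.
- **That people who quit smoking must be removed.** The wording of Section 3.3.1 does not exempt them, but Sections 7.4.6.3 and 11.0 leave participants free to cut down or quit, and Aim 3 analyses quit success. They appear to be meant to stay.

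**What to change.** Amend Section 3.3.2 so that anyone who stops study cigarettes, through inability or unwillingness, is asked, where they agree, to complete MRI visit 2 and Remote visit 3 at the scheduled week 6 (± 5 days) and the week-18 survey. State in Section 8.3 that they are analysed in their assigned arm, with a sensitivity analysis limited to participants still smoking study cigarettes.

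The cost is a short amendment. Every assessment is already in the schedule. The downside is a few scans and calls from people off product, which may dilute the on-product contrast; the sensitivity analysis keeps that estimate available. If enrolment has already closed, the assigned-arm analysis of whatever data exist, with removals reported by arm and reason, is still possible.
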